8.3.1.1. Reporting SAEs to Pfizer Safety

All SAEs occurring in a participant during the active collection period as described in [Section 8.3.1](#) are reported to Pfizer Safety on the CT SAE Report Form immediately upon awareness and under no circumstance should this exceed 24 hours, as indicated in [Appendix 3](#). The investigator will submit any updated SAE data to the sponsor within 24 hours of it being available.

8.3.1.2. Recording Nonserious AEs and SAEs on the CRF

All nonserious AEs and SAEs occurring in a participant during the active collection period, which begins after obtaining informed consent as described in [Section 8.3.1](#), will be recorded on the AE section of the CRF.

The investigator is to record on the CRF all directly observed and all spontaneously reported AEs and SAEs reported by the participant.

8.3.2. Method of Detecting AEs and SAEs

The method of recording, evaluating, and assessing causality of AEs and SAEs and the procedures for completing and transmitting SAE reports are provided in [Appendix 3](#).

Care will be taken not to introduce bias when detecting AEs and/or SAEs. Open-ended and nonleading verbal questioning of the participant is the preferred method to inquire about AE occurrences.

8.3.3. Follow-up of AEs and SAEs

After the initial AE/SAE report, the investigator is required to proactively follow each participant at subsequent visits/contacts. For each event, the investigator must pursue and obtain adequate information until resolution, stabilization, the event is otherwise explained, or the participant is lost to follow-up (as defined in [Section 7.3](#)).

In general, follow-up information will include a description of the event in sufficient detail to allow for a complete medical assessment of the case and independent determination of possible causality. Any information relevant to the event, such as concomitant medications and illnesses, must be provided. In the case of a participant death, a summary of available autopsy findings must be submitted as soon as possible to Pfizer Safety.

Further information on follow-up procedures is given in [Appendix 3](#).

8.3.4. Regulatory Reporting Requirements for SAEs

Prompt notification by the investigator to the sponsor of an SAE is essential so that legal obligations and ethical responsibilities towards the safety of participants and the safety of a study intervention under clinical investigation are met.

The sponsor has a legal responsibility to notify both the local regulatory authority and other regulatory agencies about the safety of a study intervention under clinical investigation. The sponsor will comply with country-specific regulatory requirements relating to safety reporting to the regulatory authority, IRBs/ECs, and investigators.

Investigator safety reports must be prepared for SUSARs according to local regulatory requirements and sponsor policy and forwarded to investigators as necessary.

An investigator who receives SUSARs or other specific safety information (eg, summary or listing of SAEs) from the sponsor will review and then file it along with the SRSD for the study and will notify the IRB/EC, if appropriate according to local requirements.

8.3.5. Exposure During Pregnancy or Breastfeeding, and Occupational Exposure

Exposure to the study intervention under study during pregnancy or breastfeeding and occupational exposure are reportable to Pfizer Safety within 24 hours of investigator awareness.

8.3.5.1. Exposure During Pregnancy

An EDP occurs if:

- A female participant is found to be pregnant while receiving or after discontinuing study intervention.
- A female is found to be pregnant while being exposed or having been exposed to study intervention due to environmental exposure. Below are examples of environmental exposure during pregnancy.
- A female family member or healthcare provider reports that she is pregnant after having been exposed to the study intervention by ingestion, inhalation, or skin contact.

The investigator must report EDP to Pfizer Safety within 24 hours of the investigator's awareness, irrespective of whether an SAE has occurred. The initial information submitted should include the anticipated date of delivery (see below for information related to termination of pregnancy).

- If EDP occurs in a participant, the investigator must report this information to Pfizer Safety on the CT SAE Report Form and an EDP Supplemental Form, regardless of whether an SAE has occurred. Details of the pregnancy will be collected after the start of study intervention and until 28 days after last dose, or 5 terminal half-lives after the last dose, whichever is longer.
- If EDP occurs in the setting of environmental exposure, the investigator must report information to Pfizer Safety using the CT SAE Report Form and EDP Supplemental Form. Since the exposure information does not pertain to the participant enrolled in the study, the information is not recorded on a CRF; however, a copy of the completed CT SAE Report Form is maintained in the investigator site file.

Follow-up is conducted to obtain general information on the pregnancy and its outcome for all EDP reports with an unknown outcome. The investigator will follow the pregnancy until completion (or until pregnancy termination) and notify Pfizer Safety of the outcome as a follow-up to the initial EDP Supplemental Form. In the case of a live birth, the structural integrity of the neonate can be assessed at the time of birth. In the event of a termination, the reason(s) for termination should be specified and, if clinically possible, the structural integrity of the terminated fetus should be assessed by gross visual inspection (unless preprocedure test findings are conclusive for a congenital anomaly and the findings are reported).

Abnormal pregnancy outcomes are considered SAEs. If the outcome of the pregnancy meets the criteria for an SAE (ie, ectopic pregnancy, spontaneous abortion, intrauterine fetal demise, neonatal death, or congenital anomaly, the investigator should follow the procedures for reporting SAEs. Additional information about pregnancy outcomes that are reported to Pfizer Safety as SAEs follows:

- Spontaneous abortion including miscarriage and missed abortion;
- Neonatal deaths that occur within 1 month of birth should be reported, without regard to causality, as SAEs. In addition, infant deaths after 1 month should be reported as SAEs when the investigator assesses the infant death as related or possibly related to exposure to the study intervention.

Additional information regarding the EDP may be requested by the sponsor. Further follow-up of birth outcomes will be handled on a case-by-case basis (eg, follow-up on preterm infants to identify developmental delays). In the case of paternal exposure, the investigator will provide the participant with the Pregnant Partner Release of Information Form to deliver to his partner. The investigator must document in the source documents that the participant was given the Pregnant Partner Release of Information Form to provide to his partner.

8.3.5.2. Exposure During Breastfeeding

An exposure during breastfeeding occurs if:

- A female participant is found to be breastfeeding while receiving or after discontinuing study intervention.
- A female is found to be breastfeeding while being exposed or having been exposed to study intervention (ie, environmental exposure). An example of environmental exposure during breastfeeding is a female family member or healthcare provider who reports that she is breastfeeding after having been exposed to the study intervention by inhalation or skin contact.

The investigator must report exposure during breastfeeding to Pfizer Safety within 24 hours of the investigator's awareness, irrespective of whether an SAE has occurred. The information must be reported using the CT SAE Report Form. When exposure during breastfeeding occurs in the setting of environmental exposure, the exposure information does not pertain to the participant enrolled in the study, so the information is not recorded on a CRF. However, a copy of the completed CT SAE Report Form is maintained in the investigator site file.

An exposure during breastfeeding report is not created when a Pfizer drug specifically approved for use in breastfeeding women (eg, vitamins) is administered in accord with authorized use. However, if the infant experiences an SAE associated with such a drug, the SAE is reported together with the exposure during breastfeeding.

8.3.5.3. Occupational Exposure

An occupational exposure occurs when a person receives unplanned direct contact with the study intervention, which may or may not lead to the occurrence of an AE. Such persons may include healthcare providers, family members, and other roles that are involved in the trial participant's care.

The investigator must report occupational exposure to Pfizer Safety within 24 hours of the investigator's awareness, regardless of whether there is an associated SAE. The information must be reported using the CT SAE Report Form. Since the information does not pertain to a participant enrolled in the study, the information is not recorded on a CRF; however, a copy of the completed CT SAE Report Form is maintained in the investigator site file.

8.3.6. Cardiovascular and Death Events

Not applicable.

8.3.7. Disease-Related Events and/or Disease-Related Outcomes Not Qualifying as AEs or SAEs

Not applicable.

8.3.8. Adverse Events of Special Interest

Not applicable.

8.3.8.1. Lack of Efficacy

Not applicable in Part 1. For Part 2 participants that do not gain clinical benefit following study intervention administration, lack efficacy should be captured as an AE.

8.3.9. Medical Device Deficiencies

Not applicable.

8.3.10. Medication Errors

Medication errors may result from the administration or consumption of the study intervention by the wrong participant, or at the wrong time, or at the wrong dosage strength.

Exposures to the study intervention under study may occur in clinical trial settings, such as medication errors.

Safety Event	Recorded on the CRF	Reported on the CT SAE Report Form to Pfizer Safety Within 24 Hours of Awareness
Medication errors	All (regardless of whether associated with an AE)	Only if associated with an SAE

Medication errors include:

- Medication errors involving participant exposure to the study intervention;
- Potential medication errors or uses outside of what is foreseen in the protocol that do or do not involve the study participant.

Such medication errors occurring to a study participant are to be captured on the medication error page of the CRF, which is a specific version of the AE page.

In the event of a medication dosing error, the sponsor should be notified within 24 hours.

Whether or not the medication error is accompanied by an AE, as determined by the investigator, the medication error is recorded on the medication error page of the CRF and, if applicable, any associated AE(s), serious and nonserious, are recorded on the AE page of the CRF.

Medication errors should be reported to Pfizer Safety within 24 hours on a CT SAE Report Form **only when associated with an SAE**.

8.4. Treatment of Overdose

For this study, any dose of PF-07242813 greater than 1000 mg within a 24-hour time period will be considered an overdose.

The Sponsor does not recommend specific treatment for an overdose.

In the event of an overdose, the investigator should:

1. Contact the medical monitor within 24 hours.
2. Closely monitor the participant for any AEs/SAEs and laboratory abnormalities for at least 5 half-lives or 28 calendar days after the overdose of PF-07242813 (whichever is longer). Closely monitor the participant for any AEs/SAEs.
3. Document the quantity of the excess dose as well as the duration of the overdose in the CRF.
4. Overdose is reportable to Safety **only when associated with an SAE**.
5. Obtain a blood sample for PK analysis within 28 days from the date of the last dose of study intervention if requested by the medical monitor (determined on a case-by-case basis).

8.5. Pharmacokinetics

Blood samples of approximately 4 mL will be collected for measurement of serum concentrations of PF-07242813 as specified in the [SoA](#). Instructions for the collection and handling of biological samples will be provided in the laboratory manual or by the sponsor. The actual date and time (24-hour clock time) of each sample will be recorded.

The actual times for PK assessment may change, and if needed, additional PK samples may be taken at times specified by Pfizer, provided the total serum volume taken during the study does not exceed 550 mL during any period of 60 consecutive days. All efforts will be made to obtain the samples at the exact nominal time relative to dosing. Collection of samples up to and including 10 hours after dose administration that are obtained within 10% of the nominal time relative to dosing (eg, within 6 minutes of a 60-minute sample) will not be captured as a protocol deviation, as long as the exact time of the collection is noted on the source document and the CRF/DCT. Collection of samples more than 10 hours after dose administration that are obtained \leq 1 hour away from the nominal time relative to dosing will not be captured as a protocol deviation, as long as the exact time of the collection is noted on the source document and the CRF/DCT. This protocol deviation window does not apply to samples to be collected more than 10 hours after dose administration at outpatient/follow-up visits with visit windows.

CCI

Genetic analyses will not be performed on these blood samples unless consent for this was included in the informed consent. Participant confidentiality will be maintained.

Samples collected for measurement of serum concentrations of PF-07242813 will be analyzed using a validated analytical method in compliance with applicable SOPs.

The PK samples must be processed and shipped as indicated in the instructions provided to the investigator site to maintain sample integrity. Any deviations from the PK sample handling procedure (eg, sample collection and processing steps, interim storage or shipping conditions), including any actions taken, must be documented and reported to the sponsor. On a case-by-case basis, the sponsor may make a determination as to whether sample integrity has been compromised.

Drug concentration information that may unblind the study will not be reported to investigator sites or blinded personnel until the study has been unblinded.

8.6. Pharmacodynamics

CCI

8.6.1. Skin Biopsies

CCI

Briefly, index lesion sites may be located on the torso (upper and mid back, chest), abdomen, buttocks, upper arms, and upper legs. Index lesions may not be located on the scalp, face, elbows, knees, lower legs, genital area and inguinal area, intertriginous areas and lower back. Punch biopsies of the lesional and nonlesional- skin will be obtained at the time points specified in the [Schedule of Activities](#), processed, and shipped according to the instructions to be provided in a separate study manual. Skin biopsies will be sent to designated laboratories for analysis following a schedule to be determined. The shipment address and laboratory contact information will be provided to the investigator.

CCI

As skin biopsies may be associated with risk of bleeding or infection, participants will be instructed to contact the investigator or other designated site staff if they experience bleeding, warmth, swelling, tenderness, or erythema at the biopsy site; an unscheduled visit may be required for clinical assessment.

8.7. Genetics

8.7.1. Specified Genetics

Genetics (specified analyses) are not evaluated in this study.

8.7.2. Banked Biospecimens for Genetics

A 4-mL blood sample optimized for DNA isolation Prep D1 will be collected as local regulations and IRBs/ECs allow.

Banked Biospecimens may be used for research related to the study intervention(s) and atopic dermatitis or other inflammatory skin condition. Genes and other analytes (eg, proteins, RNA, nondrug metabolites) may be studied using the banked samples.

See [Appendix 5](#): Genetics for information regarding genetic research. Details on processes for collection and shipment of these samples can be found in the laboratory manual.

8.8. Biomarkers

Collection of samples for biomarker research is also part of this study.

The following samples for biomarker research are required and will be collected from all participants in this study as specified in the [SoA](#):

- Serum to monitor select anterior pituitary hormones and hormones under anterior pituitary regulatory control (Parts 1 & 2);
- Plasma to monitor for potential cytokine release (Parts 1 & 2);
- Serum or plasma for total IgE, TARC/CCL17, IL-31, IL-17A (Part 2 only);
- Whole blood for potential assessment of lymphocyte subsets (Part 2 only);
- Non-lesional and lesional skin biopsies for histology and RNA (Part 2 only).

8.8.1. Specified Gene Expression (RNA) Research

8.8.1.1. Skin Biopsies for RNA Analysis

Four (4) mm punch biopsies will be collected from non-lesional and lesional skin according to the times outlined in the [Schedule of Activities](#). The samples will be processed and preserved in buffers appropriate for bulk and single cell RNA Sequencing. **CCI**

Details on processes for collection and shipment of these samples can be found in the laboratory manual.

Samples may be stored at a facility selected by the sponsor for a maximum of 10 years (or according to local regulations) following the last participant's last visit for the study.

8.8.2. Specified Cellular Research

8.8.2.1. Skin Biopsies for Histopathology and Immuno-histopathology

Four (4) mm punch biopsies will be collected from non-lesional and lesional skin according to the times outlined in the [Schedule of Activities](#). The samples will be preserved in formalin and embedded in paraffin. Tissue sections will be stained and **CCI** [REDACTED] research into changes in tissue pathology and infiltrating cell types.

Samples may be stored at a facility selected by the sponsor for a maximum of 10 years (or according to local regulations) following the last participant's last visit for the study.

8.8.2.2. Lymphocyte Subsets

A 10-mL blood sample for measurement of lymphocyte subsets by flow cytometry will be collected according to the times outlined in the [Schedule of Activities](#). **CCI** [REDACTED] Lymphocyte subsets may include T cells, B cells, NK cells, T cell subsets (Th1, Th2, Th17) and CD1a-restricted T cells.

Details on processes for collection and shipment of these samples can be found in the laboratory manual.

Samples may be stored at a facility selected by the sponsor for a maximum of 10 years (or according to local regulations) following the last participant's last visit for the study.

8.8.3. Specified Protein Research

CCI [REDACTED]

[REDACTED]

[REDACTED]

[REDACTED]

[figure not shown]
[REDACTED]

[REDACTED]

[REDACTED]

8.8.3.5. Anterior Pituitary Hormones and Hormones under Anterior Pituitary Regulatory Control

CCI

Banked Biospecimens will be collected as local regulations and IRB/ECs allow.

Banked Biospecimens may be used for research related to the study intervention(s) and atopic dermatitis or other inflammatory skin conditions. Genes and other analytes (eg, proteins, RNA, nondrug metabolites) may be studied using the banked samples.

See [Appendix 5: Genetics](#) for information regarding genetic research. Details on processes for collection and shipment of these samples can be found in the lab manual.

CCI

8.10. Health Economics

Health economics/medical resource utilization and health economics parameters are not evaluated in this study.

9. STATISTICAL CONSIDERATIONS

Detailed methodology for summary and statistical analyses of the data collected in this study is outlined here and further detailed in a SAP, which will be maintained by the sponsor. The SAP may modify what is outlined in the protocol where appropriate; however, any major modifications of the primary endpoint definitions or their analyses will also be reflected in a protocol amendment.

9.1. Estimands and Statistical Hypotheses

The primary estimand (for secondary endpoint EASI) will be the population average treatment effect on percent change from baseline in EASI score relative to placebo at Week 6 in the absence of prohibited medication. All observations after the initiation of prohibited medication will be set to missing. Missing data from all causes, including post-prohibited

medication use will be imputed in the PF-07242813 dose arms using a jump to control method using the distribution of the placebo group. Participants with inadequate compliance will have their recorded EASI scores used as-is in the analysis. The population based treatment effect will be the differences in the percent change from baseline in each treatment arm compared to the corresponding vehicle.

The secondary estimand **CCI** [REDACTED] will be the estimated population average treatment effect on the rates of IGA response (participants with a score of 0 or 1 and a 2 point or greater decrease from baseline) at time points specified in [Schedule of Activities](#). This is a composite estimand where success is defined as achievement of an IGA response as defined above while remaining on study, providing data and not taking prohibited medication; lack of compliance or adverse events will not be counted as a failure. The population based treatment effect will be the differences in the proportions of success in each treatment arm compared to the placebo. EASI-50, EASI-75, EASI-90 and other EASI scores will be treated in a similar manner.

CCI
[REDACTED]

9.2. Sample Size Determination

9.2.1. Healthy Participant Single Ascending and Multiple Dose (Part 1)

A sample size of approximately 52 healthy participants in 8 SAD cohorts (36 randomized to single PF-07242813 dose and 16 randomized to placebo) and up to 40 healthy participants in 5 MAD cohorts (30 randomized to multiple doses of PF-07242813 and 10 randomized to placebo) is not based on statistical considerations. The sample size was based on the clinical consideration to provide safety and tolerability information and on the need to minimize exposure to healthy participants at each dose level. In addition, 1 cohort of approximately 5 healthy Japanese participants (4 PF-07242813: 1 placebo) will be included and this sample size has been judged sufficient to obtain preliminary evaluation of safety, tolerability and PK data in this population. No formal inferential statistics will be applied to the safety, pharmacodynamic or pharmacokinetic data.

Participants who discontinue prior to completion of the study for other than safety reasons may be replaced, at the discretion of the investigator and sponsor.

9.2.2. Atopic Dermatitis Cohorts (Part 2)

The sample size calculation is based on the secondary endpoint (percent change from baseline in EASI score at Week 6). A total of 24 randomized participants with a randomization ratio of 2:1 into the treatment and placebo group will provide approximately 80% power to detect a difference of 50 in percent change from baseline with a common standard deviation 46% between PF-07242813 and the placebo arm with 1-sided alpha=0.05.

Cohort 9 will enroll 24 adult participants with moderate to severe AD.

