9.4.1. Efficacy Analyses (Part 2 Only)

Endpoint	Statistical Analysis Methods
Secondary (percent change from baseline)	A landmark analysis using analysis of covariance of percent change from baseline in EASI, adjusting for the baseline EASI score, to estimate the effect of the initially randomized treatment in the absence of prohibited medication. The analysis will use the mITT analysis set. Missing data due to any cause including censoring due to initiation of prohibited medication will be imputed using the corresponding vehicle arm, missing data in a vehicle arm will be imputed using data from the vehicle arm assuming data are missing at random (MAR). The analysis will combine the results from the multiple imputations using Rubin's rule's as implemented in SAS PROC MIANALYZE.
CCI	[REDACTED]
[REDACTED]	[REDACTED]

[REDACTED]

[REDACTED]

[REDACTED]

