5.1.2. Part 2 - Atopic Dermatitis Participants

Statistical inference will be made on the secondary endpoint: (percentage change from baseline in EASI score at Week 6). The null hypothesis is that there is no difference between the treatment group and the placebo group. The alternative hypothesis is that the treatment group (PF-07242813 arm) is superior to the placebo group at Week 6. The study will be considered positive, if this null hypothesis is rejected.

The sample size calculation is based on the secondary endpoint (percent change from baseline in EASI score at Week 6). A total of 24 randomized participants with a randomization ratio of 2:1 into the treatment and placebo group will provide approximately 80% power to detect a difference of 50 in percent change from baseline with a common standard deviation 46% between PF-07242813 and the placebo arm with 1-sided alpha=0.05.

Cohort 9 will enroll 24 participants with moderate to severe AD at the MTD.

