5.3.2. Efficacy Data

The following patient level data descriptions are also required for defining the pre-specified analyses:

Defined Analysis Data set (at the data level) – endpoint specific	Description
Primary Estimand Continuous Endpoint Set	
This set will include all patients in the mITT population. All data for a subject after the initiation of prohibited medications will be set to missing.
 
Note the primary estimand requires multiple imputation which will be performed on this dataset, the multiple imputations themselves will not be saved in the database, however, the SAS specifications and random number seed will be.

Secondary Estimand Categorical Endpoint Set	
This set will include all patients in the mITT population. All data for a subject after the initiation of prohibited medications, withdrawal of either study drug or the study itself will be set to a failure. Any other additional missing data will be recorded as a failure. Subjects will have either a success or failure in the dataset for all scheduled visits.

Observed Efficacy Set	
This set will include all patients in the mITT population and all observed data and includes all data recorded from the CRF pages. No data will be set to missing or modified from the original CRF record.

The primary analysis will use the primary estimand continuous endpoint set. For each landmark analysis (eg, Cross sectional analysis by week) missing data will be imputed using a control-based imputation method. PROC MI will first be called at the visit and a control-based method (implemented with the missing not at random (MNAR) option) will impute missing vehicle observations under the assumption data are missing at random (MAR) and impute missing treatment observations assuming they are similar to corresponding vehicle patients. Imputation will use the full conditional specification (FCS) method, the imputed data for the treatment and placebo arms will be combined for the analysis.

Summaries of continuous data will use the observed data only and no additional considerations are needed.

Analysis of binary data will use the Secondary Estimand Categorical Endpoint Set. This dataset by definition has no missing data since all missing values will have been set to a failure. Summaries will use the Observed Efficacy Set and will report results on an observed case (OC) basis.

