6.2.1.1. Main Analysis

- Estimand strategy: Estimand E1 ([Section 3.1.2](#)). This estimand is intended to provide an estimate of the treatment effect in the absence of prohibited medication use in a population that may or may not be fully compliant with the treatment.
- Analysis set: mITT ([Section 4](#)) using data prepared in the description of the Primary Estimand Continuous Endpoint Set.
- Analysis methodology: Percent change from baseline will be analyzed using an ANCOVA with the observed (or imputed) Week 6 percentage change from baseline EASI score as the dependent variable with treatment arm and baseline EASI score as the independent variables.
- Intercurrent events and missing data: Data after study drug discontinuation and prohibited medication will be excluded and set to missing. Missing data which will be multiply imputed using a control-based strategy as described in ([Section 5.3.2](#)). Hundred (100) imputed datasets will be used in the analysis and results combined using PROC MIANALYZE.
- The least-squares (LS) means, the 90% confidence interval for the LS means, the difference between the LS means for each pair of treatment groups, and the corresponding 90% confidence interval will be presented for percent change from baseline in EASI score.

CCI

CCI

[figure not shown]450 and \leq 480	>480 and \leq 500	>500
Increase from baseline in QTcF (msec)	>30 and \leq 60	>60	

Categories for PR and QRS

PR (ms)	max. \geq 300	
PR (ms) increase from baseline	Baseline $>$ 200 and max. \geq 25% increase	Baseline \leq 200 and max. \geq 50% increase
QRS (ms)	max. \geq 140	
QRS (ms) increase from baseline	\geq 50% increase	

Categories for Vital Signs

Systolic BP (mm Hg)	min. $<$ 90	
Systolic BP (mm Hg) change from baseline	max. decrease \geq 30	max. increase \geq 30
Diastolic BP (mm Hg)	min. $<$ 50	
Diastolic BP (mm Hg) change from baseline	max. decrease \geq 20	max. increase \geq 20
Supine pulse rate (bpm)	min. $<$ 40	max. $>$ 120

Measurements that fulfill these criteria are to be listed in report.

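### Does pooling the placebo-based imputations by Rubin's rules make the Week 6 EASI test so conservative that the plan needs a different standard error?

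*Protocol*

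**What the plan says.** Protocol 9.2.2 and SAP 5.1.2 give the same calculation: 24 participants, 2:1, which "will provide approximately 80% power to detect a difference of 50 in percent change from baseline with a common standard deviation 46" percentage points at 1-sided alpha 0.05. SAP 5.1.2 attaches the verdict to this test: "The study will be considered positive, if this null hypothesis is rejected".

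Protocol 9.1 says that missing values from any cause, including those blanked after prohibited medication, are "imputed in the PF-07242813 dose arms using a jump to control method using the distribution of the placebo group". SAP 5.3.2 repeats the rule ("impute missing treatment observations assuming they are similar to corresponding vehicle patients"); placebo gaps are imputed under MAR. On pooling, Protocol 9.4.1 says: "The analysis will combine the results from the multiple imputations using Rubin's rule's as implemented in SAS PROC MIANALYZE". SAP 6.2.1.1 adds: "Hundred (100) imputed datasets will be used in the analysis and results combined using PROC MIANALYZE", "and the corresponding 90% confidence interval will be presented for percent change from baseline in EASI score".

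The code in SAP Appendix 6 uses predictive mean matching (PMM, k=5) from placebo donors and calls MIANALYZE without a complete-data df, so the default df apply. Neither document states an expected censoring rate.

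**The concern.** Under jump-to-control, a censored active participant receives a placebo-like value. The estimate is then close to f × D, where f is the share of the active arm with usable Week 6 data and D is the ANCOVA difference among observed participants. Losing active values shrinks this estimate towards zero and does not widen its repeated-sampling spread. Rubin's variance, T = W + (1 + 1/M)B, still adds between-imputation variance B, drawn from at most 8 placebo donors. The reported SE can therefore exceed the true SD, so the level falls below 5%, the 90% interval is too wide and power drops. In a 24-participant signal-finding cohort the cost would be a missed signal. The obvious remedy is SE = f × SE(D), which gives the same p-value as an ANCOVA on observed participants.

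**Working it through.** **Inputs.** 16 active and 8 placebo, difference 50, SD 46, 1-sided 0.05 (Protocol 9.2.2); imputation and pooling as above, M = 100. Assumed: normal percent change, and loss counts chosen as scenarios because none are documented. Losses are written active+placebo.

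**1. The plan's own figure.** SE = 46 × √(1/16 + 1/8) = 19.9; 50/19.9 = 2.51; Φ(2.51 − 1.645) = 0.81. The exact noncentral t gives 0.78. The stated figure of about 80% stands for complete data.

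**2. Values lost at random, 2+1.** f = 14/16 = 0.875, so the expected estimate is 0.875 × 50 = 43.75 (simulated: about 44). Its simulated SD is about 19.5, while the mean Rubin SE is 23.6 to 24.9, a ratio of 1.23 to 1.26 by the matching pairs (PMM and regression imputation, planned effect). With the coded PMM and default df, percent-change ANCOVA and 6,000 simulated trials per cell:

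| Lost | Level | Power, planned | Power, observed participants |
|---|---|---|---|
| 1+0 | 4.0% | 73% | 75% |
| 2+1 | 3.1% | 61% | 71% |
| 3+1 | 2.2% | 52% | 69% |
| 4+1 | 1.7% | 40% | 69% |

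So the mechanism is real when active values go missing at random. Small-sample df lower the planned figures further, but the code does not request them.

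**3. Placebo values lost, none active.** Under PMM with default df the level is 6.1% at 0+1 and 6.4 to 7.0% at 0+2. With regression imputation it is 4.5% at 0+2. The conservatism comes from active-arm loss and is not a general property of the plan.

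**4. Loss that follows poor response.** Protocol 6.5.3 allows prohibited treatment when the investigator judges it necessary for the underlying disease. Random loss is therefore the less likely pattern. Censoring the worst responders with no drug effect (a deliberately extreme rule) gives these levels:

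| Worst responders lost | Planned test, default df | f × SE(D) test |
|---|---|---|
| 2+1 | about 5% | 7 to 8% |
| 3+1 | 5 to 6% | 11% |
| 2+0 | 8 to 10% | 14% |

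Dropping the worst active responders flatters the observed active mean and trims the residual spread. At 2+1 the f × SE(D) formula reports 15.9 against a real SD of 18.6. The extra width in Rubin's SE offsets this, and planned power there is 69 to 72%.

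**5. How the alternative SE behaves.** Using f × 46 × √(1/n_active + 1/n_placebo):
- complete data: 1 × 19.9 = 19.9
- 14 v 7 observed: 0.875 × 46 × √(1/14 + 1/7) = 18.6
- 13 v 7 observed: 0.8125 × 46 × √(1/13 + 1/7) = 17.5

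The stated uncertainty falls as active-arm data are lost.

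**6. Keeping the imputations.** A jackknife SE gives 63 to 65% power at 2+1, against 60 to 61% for the coded analysis: a gain of about 2 to 5 points.

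**7. Text and code.** SAP 5.3.2 says "Imputation will use the full conditional specification (FCS) method", whereas the code uses a monotone PMM statement and models absolute change. On absolute change the 2+1 gap is 58 to 62% against 67%. Neither difference alters the conclusion.

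**The case for a change.** The strongest case for acting is that the effect reproduces under both regression and PMM imputation and under either df rule. At 2+1 the Rubin SE (24 to 25) exceeds even the SE of the undiluted difference in the 21 observed participants (about 22). The loss is therefore more than the price of missing data. Censoring is foreseeable: Protocol 6.5.2.2 anticipates prohibited treatment before Week 6, replacement is optional, and a dosed participant stays in the mITT set. The gain from a repeated-sampling SE also grows with loss. At 4+1 a jackknife gives 59% power (regression imputation), against 40% for the coded analysis.

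All of this stands for loss unrelated to outcome. It does not carry over to loss driven by poor response, where the alternative test exceeds 5% and the planned test stays nearer to it. A p-value identical to the observed-participant ANCOVA would also mean that the assumption of no benefit after prohibited medication no longer affects the decision in SAP 5.1.2. Whether the SE should shrink as active data disappear is disputed among statisticians, and Rubin's rules are a standard, prespecified choice. Heavy loss is not expected from the design: a single dose, advice to defer other treatment past Week 6, and possible replacement. SAP 5.2.3 also plans an MMRM through Week 6 with differences, p-values and 90% intervals, which gives a second view of the same data.

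**Conclusion.** No change is needed. The stated power is correct for complete data. With 2 active and 1 placebo values lost at random, the coded analysis has a level of about 3% and power of about 60%, roughly 10 points below the observed-participant test. With one active loss the gap is about 2 points. Under PMM with placebo-only loss the direction reverses. When the losses are the worst 2+1 responders, the planned test is close to 5% and the alternative is not.

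The planned pooling errs mainly towards caution, and the alternative buys power with a risk of false positives in the situation the protocol itself describes. That is a fair trade-off. A note that 80% assumes usable Week 6 EASI in all 24, or a stated df rule, would only record what a reader can already infer from the calculation and the code. The sizes rest on normal outcomes, assumed loss counts and an extreme poor-responder rule. A documented high rate of active-arm loss clearly unrelated to response would strengthen the case for a supportive repeated-sampling SE, but the documents give no such rate.
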